5. The link will take you to the Project Summary page for the project. Follow the PI instructions for items #4 and #5 above.

If you are a contact (member of research team) and you wish to access minutes or approved materials:

1. Login to the regular myIRB website as yourself.
2. Scroll to the listing of "Projects" at the bottom of your Inbox page.
3. Change the filter for the Project to show projects where you are a research team member and click "Go" on the filter.
4. Click on the IRB number for the approved project.
5. The link will take you to the Project Summary page for the project. Follow the PI instructions for items #4 and #5 above.

E1 Overview or Design Summary

ED patients will be approached for informed consent if they meet selection criteria. Patients who consent to be in the trial will be randomized to either morphine (0.1mg/kg maximum dose of 10 mg) or ketamine (0.4 mg/kg, maximum dose of 40 mg). During the consent process, patients can be pretreated for pain with fentanyl IV up to 100mcg. Patients will not be given their assigned pain medication until at least thirty minutes after administration of any fentanyl to avoid overlapping effect of fentanyl with ketamine or morphine.

~~ED patients will be approached for informed consent if they meet selection criteria. Patients who consent to be in the trial will be randomized to either morphine (0.1mg/kg maximum dose of 10 mg) or ketamine (0.4 mg/kg, maximum dose of 40 mg).~~

PHARMACY NOTIFICATION

The research pharmacy will be notified of a potential study participant so they can prepare to randomize the participant using a random number generator. Odd numbered participants will receive ketamine and even numbered participants will receive morphine. Participants in the low dose ketamine arm will receive 0.4 mg/kg IV of ketamine (40 mg maximum). Participants in the opioid arm will receive 0.1 mg/kg of morphine up to 10 mg.

PHARMACY FORMULATION

Upon the completion of consent, the pharmacy will be notified to draw up the appropriate medication and send the medication to the Emergency Department. The study medication will be in identical appearing unmarked syringes, so that neither the study team nor the study subject will know which medication is being administered.

VITAL SIGN COLLECTION

The research coordinator will then complete page one of the Ketamine Data Form. This includes the participant's medical history, including a history of drug abuse, or prior narcotic use, a description of the injury, prior medications given to the subject for this injury either by EMS or in the emergency department, baseline vital signs (prior to study drug administration) and the time of study drug administration. Page 2 includes the baseline (pre study drug administration) visual analog pain scale that the participant will complete.

MEDICATION ADMINISTRATION

If the participant has not yet had an IV placed, one will be placed by the nurse caring for the participant at this time. Study drug will then be administered.

VITAL SIGN COLLECTION

The participant's heart rate, blood pressure, respiratory rate and oxygenation saturation (by pulse oximetry) will be collected every 5 minutes for the first 30 minutes, and every 10 minutes

for the next 30 minutes. The study will terminate at the end of 60 minutes and a final set of vital signs will be recorded at that point on Page 3 of the Ketamine Data Form.

REEVALUATION & EXIT SURVEY

The participant will be asked to complete repeat visual analog pain scales at 15, 30, and 60 minutes following study drug administration. The VAS will be administered by a second study coordinator, who has been blinded to the vital sign information, since blood pressure response may allow unblinding to occur. The participant will not have access to their original score for comparison. The study coordinator will then complete the post treatment survey on Page 5. The participant will continue to receive standard care by the emergency department physicians and nurses to ensure adequate relief of pain, appropriate treatment of the underlying pathology, hemodynamic and neuropsychiatric stability, and appropriate diagnostic evaluation, disposition, and follow-up. Any adverse events that occur during the continued treatment of the participant until either admission or discharge will be recorded.

RESCUE MEDICATION

Subjects that do not obtain adequate pain relief within 15 minutes of study drug administration will be offered rescue medication with intravenous morphine sulphate at the same weight-based dose (0.01mg/kg; maximum 10 mg)

TREATMENT OF ADVERSE EVENTS AND SERIOUS ADVERSE EVENTS

Adverse events and serious adverse events will be noted on the data form and treated by the study physician or the primary treating physician as medically indicated.

E2 Subject Selection and Withdrawal

2.a Inclusion Criteria

Patients over the age of 18 presenting with long-bone fractures are eligible for enrollment. Eligible long-bone fractures include fractures of the shaft of the humerus, radius, ulna, femur, tibia, and fibula.

2.b Exclusion Criteria

Patients with injuries older than 24 hours will be excluded. Patients with avulsion fractures will be excluded. Patients with a history of substance abuse, chronic opioid dependence, pregnancy, intoxication, allergy to ketamine or opioids, and those that cannot consent (e.g. active mental disease preventing them from having capacity to consent) will be excluded. Any patients with hemodynamic instability defined as systolic blood pressure > 180 mmHg or < 100 mmHg, heart rate > 130 bpm, respirations < 10 rpm, or oxygen saturations on room air < 90% shall also be excluded. In addition, any patient that received a narcotic analgesic aside from fentanyl within the last 2 hours will be excluded.

2.c Study Termination

Subjects can terminate their participation in the study at any time. The alternative to continuing in the study is to have the pain treated by emergency physicians and staff as per usual care. The study physician may terminate the study prior to the specified endpoint when deemed medically prudent to do so.

2.d Ethical Considerations

Current research has investigated the effectiveness of ketamine as an analgesic in the Emergency Department. Much of that research is observational which limits the conclusions that can be drawn. While ketamine's mechanism of action would be consistent with an agent that can result in analgesia, we would like to conduct a randomized, blinded trial to determine if ketamine is as effective as an analgesic as morphine. We believe given the pharmacologic properties of ketamine, and prior published research, that ketamine is an effective analgesic so this research is important and ethical. All data will be collected by trained research staff and kept in a locked office to minimize the chance of lost data.

2.e Subject Recruitment Plans and Consent Process

Patients who are identified as potential study participants will be approached by the research coordinators regarding informed consent. The purpose of the study, study procedures, and associated risks and benefits will be explained to the potential subject. Following this, subjects will have 10 minutes to review the consent form on their own and if they agree to participate in the study, the consent form will be completed.

2.f Randomization Method and Blinding

Randomization will occur in the research pharmacy using opaque, sealed envelopes. Twenty participants will be randomized into each arm. Participants in the LDK arm will receive 0.4 mg/kg IV of ketamine (40 mg maximum). Participants in the opioid arm will receive 0.1 mg/kg of morphine up to 10 mg. Medications will be prepared by the pharmacy and delivered to the treating nurse in identical syringes. Study drug will be blinded to the research team and the study participant.

2.g Risks and Benefits

Patient will be exposed to medical risks in both conditions. Patients exposed to morphine will be at risk for hypotension, respiratory depression, altered mental status and possible allergic reaction. Patients exposed to ketamine will be at risk for hypertension, dysphoria and in rare cases laryngospasm and emergence reaction. These side effects are well known by practitioners since both of these drugs are regularly given in the Emergency Department. Patients may also be at risk for inadequate pain control in either condition.

2.h Early Withdrawal of Subjects

Participants will be told they have the right to withdraw from the study at anytime for any reason. Participants will also be taken out of the study early if the physician, nurse or research coordinator decides that the participant is at risk for a life-threatening event. Since this study does not include any outpatient follow-up, we do not anticipate early withdrawal to be a problem.

2.i When and How to Withdraw Subjects

The research coordinator will continually monitor the participant, and the nurses and physicians will be able to remotely monitor the participant's vital signs at the telemetry station. If a life-threatening event is identified, the participant will be resuscitated as deemed appropriate by the physician caring for the participant.

2.j Data Collection and Follow-up for Withdrawn Subjects

Due to the short duration of the study (60 minutes), we do not anticipate early withdrawal to be a problem. Participants who have inadequate pain relief and require rescue medication, or who have adverse events that require other treatment will have their data included, even if study personnel are unable to complete the follow-up VAS scores at 15, 30, or 60 minutes.

Study Drug

2.k Description

Ketamine is a dissociative agent that is thought to modulate pain by binding to NMDA receptors. Participants assigned to the ketamine arm will be given 0.4 mg/kg IV of ketamine (40 mg maximum).

Morphine is an opioid that acts on opioidergic receptors to modulate pain. Participants in the opioid arm will receive 0.1 mg/kg IV of morphine (10 mg maximum).

2.l Treatment Regimen

The study is designed to compare a one-time dose only. Therefore study medication administration will occur once following the baseline pain and vital sign assessment.

Assignment of Subjects to Treatment Groups

Participants will be assigned to either the ketamine arm or the morphine arm in the pharmacy by random number generator. Participants and all study personnel will be blinded to the assignment.

2.m Preparation and Administration of Study Drug

Once participants are in the process of being consented, the pharmacy will be notified to prepare the drug. The drug will then be sent to the Emergency Department for administration.

2.n Subject Compliance Monitoring

Participants will be given the drug intravenously by the emergency department staff nurse assigned to their care. The research coordinator will monitor the participant's vital signs, pain relief, and any side effects during the duration of the study. Since medication is only given one time, non-compliance will not be an issue.

Prior and Concomitant Therapy

Participants will be excluded from the study if they are found to be chronic users of either prescribed or illicit opioids or opiates.

2.o Packaging

Study drug will be packaged by the pharmacy in identical looking syringes so as to maintain blinding. This is a question for the pharmacy. I will email [name] about this.

2.p Blinding of Study Drug

As above

2.q Receiving, Storage, Dispensing and Return

The pharmacy will transport the study medication to the emergency department. If the patient withdraws from the study, the medication can be returned to the pharmacy.

F Study Procedures

F1 Screening for Eligibility

Participants will be identified in the Emergency Department waiting room as a potential candidate for the study by nurses, physicians and the research coordinator on duty. If a long bone fracture is deemed highly likely or if a long bone fracture has been identified by X-ray, the injury occurred within 24 hours, and the patient is conscious and alert and hemodynamically stable they will be approached for consent.

F2 Schedule of Measurements

Participants will have vital signs collected immediately prior to administration of the medication to which they are assigned. Vital signs (heart rate, respiratory rate, blood pressure, and pulse oximetry) will be recorded every 5 minutes for the first 30 minutes following the administration of study drug, and then every 10 minutes until study

completion (60 minutes post medication administration). Pain severity will be assessed immediately prior to administration of medication via the VAS and at 15, 30 and 60 minutes following medication administration..

F3 Visit 1

The participant will only be treated on the first encounter in the Emergency Department.

F4 Visit 2 etc.

N/A

F5 Safety and Adverse Events

We will monitor and record for changes in vital signs including hypotension, hypertension, tachycardia, bradycardia, respiratory depression. We will also monitor for nausea and vomiting, laryngospasm, and emotional and psychological effects (emergence reactions).

5.a Safety and Compliance Monitoring

Participants will receive only one dose of study drug, thus compliance will not be an issue. Participants will be monitored continuously for alterations in vital signs, or any other adverse events during the entirety of the study.

5.b Medical Monitoring

Both of these medications are commonly used in the emergency department setting, and have a good safety record. Nonetheless, AEs, and SAEs may occur. Any adverse event directly linked to administration of either ketamine or morphine that results in permanent disability or death will result in the cessation of the entire study.

Further, after every 10 patients are enrolled, all AE's will be reviewed by an independent expert. If there is a high frequency of adverse events that cause great distress to participants or that results in many participants ending their participation, the study will be terminated.

If five or more serious adverse events (SAE's) occur, we will have an institutional Data and Safety Monitoring Board perform an interim analysis to determine if there is a safety issue.

i Independent expert to monitor

We will perform an interim analysis on the AE's after every 10 patients. If we identify five or more SAE's, we will suspend the study until we have an institutional Data and Safety Monitoring Board perform an interim analysis to determine if there is a safety issue.

ii Institutional Data and Safety Monitoring Board

We will assign 3 independent experts to an institutional DSMB.

iii Independent Data and Safety Monitoring Board

We do not plan to have an independent DSMB

5.c Definitions of Adverse Events

Any untoward medical occurrence (signs, symptoms, lab abnormalities) associated with the use of study drug, whether or not considered drug related.

Serious Adverse Events (SAE's):

Any Adverse Event that in the opinion of the Investigator or Sponsor results in:

Death or is life-threatening (immediate risk of death)

Hospitalization or prolongation of existing hospitalization

Persistent or significant incapacity or substantial disruption of the ability to conduct normal life functions (aka disability)

In addition, we have defined the following vital sign and behavioral abnormalities as SAE's:

Apnea: period of no respirations for greater than 20 seconds

Hypotension: systolic blood pressure < 90 mmHg

Hypertension: systolic blood pressure > 180 mmHg

Laryngospasm: Reflexive closure of the vocal cords that results in inability to ventilate.

Emergence Reaction: Anxiety, agitation, disorientation

Respiratory depression: respiratory rate < 8 breaths/min or sats < 92%

Bradycardia: Heart rate < 50 bpm

5.d Classification of Events

i Relationship

We will review each adverse event to see if it is associated with study drug.

The relationship of the AE to study drug will be based on temporal association, and other clinical information such as concomitant medications, pre-existing conditions, and the natural history of the disease process.

Investigator causality assessment (relationship of AE to study drug) will be categorized as: 1) Probably related 2) Possibly related 3) Unlikely related and 4) Not related.

ii Severity

Severity of the AE will be documented using the FDA categories of 1) mild, 2) moderate, 3) severe, and 4) potentially life threatening.

Expectedness

Based on past research, we believe adverse events will be rare and severe events are unlikely to occur.

5.e Data Collection Procedures for Adverse Events

The research coordinator will write down all adverse events on the data form in the designated spot. They will also report the events to the treating team.

5.f Reporting Procedures

The research coordinator will report all adverse events to the principal investigator (PI) investigator during the study. The PI will determine severity and causality. The PI will keep track of adverse events to determine if the study needs to be stopped.

5.g Adverse Event Reporting Period

This is an acute treatment trial, with a duration of one hour following study drug administration. However, any AEs that occur at any time during the entire ED stay of the study participant will be reported.

Post-study Adverse Event

The duration of the drugs used in this study will not exceed the time the participant is monitored.

F6 Study Outcome Measurements and Ascertainment

Study outcomes involve change in participants' pain as measured by the VAS, significant changes in any vital signs collected, a list of adverse events that the participant experienced, as well as questions included in the data form assessing whether the participant would consider using the drug given to them for pain relief in the future.

G Statistical Plan

G1 Sample Size Determination and Power

Sample size for this study is based on limited funding and will serve as a pilot study looking for trends in the efficacy of morphine and ketamine to treat pain as well physiologic effects and adverse events. If the results appear promising, further funding will be requested and a full power analysis will be performed.

G2 Interim Monitoring and Early Stopping

All adverse events will be promptly reviewed by the primary research team following the participant's completion of the study. Any adverse event directly linked to administration of either ketamine or morphine that results in permanent disability or death will result in the cessation of the entire study. After every 10 patients are enrolled, adverse event information will be reviewed by an independent expert. If there is a high frequency of

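### The arm is tied to an odd or even participant number that is never defined, so the text permits alternation or a number that reveals the arm

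*SAP*

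**What the plan says.** Allocation is described in three places in the SAP.

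- **E1, Pharmacy Notification.** The research pharmacy is told of a potential participant "so they can prepare to randomize the participant using a random number generator". The next sentence is the rule: "Odd numbered participants will receive ketamine and even numbered participants will receive morphine".
- **2.f, Randomization Method and Blinding.** "Randomization will occur in the research pharmacy using opaque, sealed envelopes. Twenty participants will be randomized into each arm".
- **Assignment of Subjects to Treatment Groups.** Here the generator returns: "Participants will be assigned to either the ketamine arm or the morphine arm in the pharmacy by random number generator". This paragraph mentions neither envelopes nor odd and even numbers. It continues: "Participants and all study personnel will be blinded to the assignment".

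Two places describe when the drug is made ready.

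- **E1, Pharmacy Formulation.** "Upon the completion of consent, the pharmacy will be notified to draw up the appropriate medication".
- **2.m.** "Once participants are in the process of being consented, the pharmacy will be notified to prepare the drug".

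On protecting the pain assessment, E1 (Reevaluation & Exit Survey) has the VAS given by a second coordinator "who has been blinded to the vital sign information, since blood pressure response may allow unblinding to occur".

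**The concern.** The odd/even sentence is the only rule in the document that links a number to an arm, and it attaches the number to participants rather than to a random draw. What the number is, when it is issued and who sees it are left open. Two things could go wrong.

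**Selection.** Under F1, nurses, physicians and the coordinator on duty identify candidates, and a patient may be approached before X-ray if a fracture is thought highly likely. Staff therefore have discretion over whom to approach. If they could foresee the next arm, that discretion could follow it, and selection bias of this kind cannot be repaired after enrolment.

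**Unblinding.** Identical syringes do not help if the participant's number gives the arm. The plan keeps vital signs from the VAS coordinator because blood pressure might reveal the drug. A visible number whose parity names the drug would reveal it more directly. Change in self-reported VAS pain is the first outcome listed in F6.

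**Working it through.** **Inputs.** Twenty per arm, 40 in total (2.f); odd gives ketamine and even gives morphine (E1). G1 bases the sample size on funding and gives no power calculation, so the only figure to check is the 20/20 split. Each reading of the rule can be tested against it.

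**Reading A: consecutive enrolment numbers 1 to 40.** There are 20 odd and 20 even numbers, so the split matches 2.f. But the sequence is strict alternation. Anyone who knows the rule and the last number knows the next arm: 40 of 40 are predictable, and no random element remains. This contradicts the random number generator in E1 and in the Assignment paragraph, and the sealed envelopes would conceal nothing.

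**Reading B: an independent random number per participant, kept in the pharmacy.** Allocation is random, and nothing is predictable or readable. The number in one arm is then Binomial(40, 0.5):

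- P(exactly 20/20) = C(40,20) / 2^40 = 0.125
- P(larger arm has 22 or more) = 2 × P(X ≥ 22) = 0.636
- P(larger arm has 24 or more) = 2 × P(X ≥ 24) = 0.268

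This reading needs a restriction to reach 20 per arm, and the text states none.

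**Reading C: a generated number that also serves as the participant's number and is visible to staff.** Nothing can be predicted from enrolment order, but up to 40 of 40 arms can be read once the number is seen. This conflicts with the blinding of all study personnel.

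| Reading | Random | Gives 20/20 unaided | Arm hidden from staff |
|---|---|---|---|
| A: enrolment number | No | Yes | No, if the rule is known |
| B: draw kept in pharmacy | Yes | Probability 0.125 | Yes |
| C: visible generated number | Yes | Probability 0.125 if draws are independent | No |

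No row meets all three stated features.

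**Benchmark: a concealed random list of 20 + 20.** With blinding intact, chance guessing gives 40 × 0.5 = 20 correct. In the worst case every earlier arm has leaked and the guesser always names the arm with more places left. The expected number correct is then

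20 + 0.5 × (2^40 / C(40,20) − 1) = 20 + 0.5 × (7.976 − 1) = 23.49 of 40, or 58.7%.

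A restricted list that leaked completely would therefore still be far less predictable than alternation.

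**Timing.** E1 has the drug drawn up once consent is complete; 2.m has it prepared while consent is under way. Unless both drugs are prepared for every patient, which no section says, 2.m requires the arm to be fixed before the patient has consented. E1 also says that it is patients who consent who are randomised. The two sections cannot both describe the procedure.

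**The case against.** The best defence is context. The sentence before the rule names a random number generator, and E1, 2.f and the Assignment paragraph all place randomisation in the pharmacy. Odd and even may simply be how the pharmacy decodes a generated number. No section says that numbers follow enrolment or that staff see them. A generator and envelopes can coexist, one making the list and the other concealing it. Operational detail may also sit in a protocol that is not at hand, and the participant completes the VAS, so a coordinator who knew the arm could influence it only indirectly. On timing, an arm fixed early but held in the pharmacy does not by itself breach concealment.

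Much of this stands. The harmless reading is plausible, generator and envelopes are not in themselves contradictory, and the harm depends on facts that the plan does not give. The timing discrepancy is a conflict of wording, not a demonstrated leak.

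The defence does not remove the point. The plan is not merely silent: it states a rule, and states it in terms of participants' numbers. The harmless reading also leaves the fixed 20 per arm unexplained, while the reading that delivers 20 per arm unaided is alternation.

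**Conclusion.** The concern holds and should be fixed. As written, the rule permits alternation or a participant number that reveals the arm, and it is not reconciled with the generator, the envelopes, the 20 per arm or the blinding.

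The size depends on how the number is issued:

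- enrolment order: 40 of 40 assignments predictable;
- random but visible to staff: none predictable from enrolment order, up to 40 of 40 readable;
- kept in the pharmacy: none predictable or readable, but the stated split is not assured.

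The first two cases assume that staff know the rule, and the second that they see the number. The conclusion concerns the text; it does not claim that the trial alternates. Confidence is high that the rule is badly stated. Whether any bias would follow cannot be judged from this document. The status as a pilot does not remove the need: G1 makes further funding depend on whether the results look promising.

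**What to change.** Delete the odd/even sentence and give the same single description in E1, 2.f and the Assignment paragraph:

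1. The research pharmacy generates a computer random list restricted to 20 per arm and is the only party to hold it.
2. The assignments are concealed in the opaque, sealed envelopes named in 2.f.
3. The next envelope is opened only after consent is complete, and 2.m is aligned with the Pharmacy Formulation wording in E1.
4. Participant numbers carry no information about the arm.

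Defining the number as generator output held in the pharmacy would settle what it means, but the restriction to 20 per arm would still have to be stated.

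The cost is a few sentences and one list, with no extra patients or staff. If the drug is at present prepared during consent, opening the envelope afterwards adds the pharmacy's preparation time before study drug. The plan does not give that time, so the pharmacy should be asked for it before the text is settled.

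### The rescue morphine dose is printed as 0.01 mg/kg, one tenth of the 0.1 mg/kg study dose it is said to equal

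*SAP*

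**What the plan says.** Rescue is triggered by lack of effect at a fixed time: "Subjects that do not obtain adequate pain relief within 15 minutes of study drug administration will be offered rescue medication". The same sentence in section E1 (Rescue Medication) then gives the dose: "rescue medication with intravenous morphine sulphate at the same weight-based dose (0.01mg/kg; maximum 10 mg". No other rescue dose appears in the text available.

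The randomized morphine dose is given four times in current text, always with the same two numbers:

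- E1, opening paragraph: patients are "randomized to either morphine (0.1mg/kg maximum dose of 10 mg) or ketamine (0.4 mg/kg, maximum dose of 40 mg".
- E1, Pharmacy Notification: "Participants in the opioid arm will receive 0.1 mg/kg of morphine up to 10 mg".
- 2.f, Randomization Method and Blinding: the same sentence as in Pharmacy Notification.
- 2.k, Description: "Participants in the opioid arm will receive 0.1 mg/kg IV of morphine (10 mg maximum".

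Two further statements bear on the consequences. E1 (Reevaluation & Exit Survey) says: "The participant will continue to receive standard care by the emergency department physicians and nurses to ensure adequate relief of pain". Section 2.j says: "Participants who have inadequate pain relief and require rescue medication, or who have adverse events that require other treatment will have their data included".

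**The concern.** The rescue sentence says in words that the dose equals one already defined, and then prints a number that does not match. Both cannot be followed. The number is an operative opioid dose, to be acted on at the bedside in patients with long-bone fractures whose study drug has not worked.

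The first stake is patient care: read by the number, rescue is a tenth of the study dose and the risk is under-treated pain. Section 2.g already names inadequate pain control as a risk in either arm.

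The second is consistency. If some staff follow the words and others the number, rescued participants get different doses. Rescue starts at about 15 minutes and rescued participants' data are kept, so this could add variation to the 30- and 60-minute VAS scores. The SAP gives nothing from which to estimate how much.

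**Working it through.** **Inputs from the SAP**

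- Rescue morphine as printed: 0.01 mg/kg, maximum 10 mg (E1, Rescue Medication).
- Study morphine: 0.1 mg/kg, maximum 10 mg (E1 opening paragraph, E1 Pharmacy Notification, 2.f, 2.k).
- Study ketamine: 0.4 mg/kg, maximum 40 mg (E1 opening paragraph).

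**Assumption.** The SAP gives no body weights; 50 to 120 kg is used for illustration.

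**Step 1: are the two doses the same?** 0.1 / 0.01 = 10. The printed rescue dose per kilogram is exactly one tenth of the study dose, so the claimed equality fails.

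**Step 2: at what weight does the cap take effect?** Weight = maximum dose / dose per kg.

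- Study morphine: 10 / 0.1 = 100 kg.
- Study ketamine: 40 / 0.4 = 100 kg.
- Rescue as printed: 10 / 0.01 = 1000 kg.

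Both study-drug caps are set to take effect at 100 kg. The rescue cap fits that pattern only if the dose is 0.1 mg/kg; at 0.01 mg/kg it can never operate. A cap that never operates is not in itself a contradiction, so this is supporting evidence. The contradiction rests on the word *same*.

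**Step 3: size in milligrams.** Dose = min(10, dose per kg × weight).

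| Weight (assumed) | At 0.01 mg/kg | At 0.1 mg/kg, max 10 mg | Ratio |
|---|---|---|---|
| 50 kg | 0.5 mg | 5 mg | 10 |
| 70 kg | 0.7 mg | 7 mg | 10 |
| 100 kg | 1.0 mg | 10 mg | 10 |
| 120 kg | 1.2 mg | 10 mg (capped) | 10 / 1.2 = 8.3 |

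**Step 4: cumulative morphine in the morphine arm if rescue is 0.1 mg/kg.** 0.1 + 0.1 = 0.2 mg/kg, at most 10 + 10 = 20 mg. With the printed figure it would be 0.1 + 0.01 = 0.11 mg/kg below 100 kg.

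**The case against.** The inconsistency itself is hard to dispute; the case on the other side is about how much it matters and how sure one can be of the intended figure.

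*The sentence signals its own correction.* The wording and the unchanged 10 mg cap lead an alert reader to 0.1 mg/kg, and standard care for pain continues whatever the rescue line says. This reduces the likely harm. It does not make a wrong opioid dose acceptable in an operative instruction.

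*A lower rescue dose may have been intended.* The four statements of 0.1 mg/kg concern the randomized dose, and in a two-arm trial *same* might mean the same in both arms. That reading leaves the 10 mg maximum without purpose, and nothing in the available text supports a lower dose. It is still a reason to ask the sponsor before changing the number.

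*The corrected figure carries its own risk.* At 0.1 mg/kg, a morphine-arm participant could receive a second full dose soon after 15 minutes, from staff blinded to what the first syringe contained. Section 2.g lists hypotension and respiratory depression as morphine risks, and 5.c counts both as serious adverse events. This point stands. The exposure follows from the plan's own wording, but it should be stated openly when the figure is corrected.

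*No bias in the result is shown.* This is also true. Rescue affects the 30- and 60-minute VAS at either dose, and correcting the digit does not remove that effect. The case rests mainly on dosing safety.

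**Conclusion.** The concern holds. The printed rescue dose contradicts the sentence it stands in and is one tenth of the study morphine dose. Followed by the number, the shortfall is tenfold up to 100 kg and 8.3-fold at 120 kg. The ratio up to 100 kg does not depend on weight; the milligram figures rest on assumed weights. That 0.1 mg/kg was meant is an inference from the word *same* and from the cap, strong but for the sponsor to confirm. The direct risk of the printed figure is under-treatment, not overdose. Because it is an operative opioid dose, it must be fixed.

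**What to change.** In E1, Rescue Medication, replace 0.01 mg/kg with 0.1 mg/kg and keep the 10 mg maximum, after the sponsor confirms that this was intended. State alongside it that a rescued morphine-arm participant may then receive up to 0.2 mg/kg in total (at most 20 mg), so that confirmation is given with that exposure in view.

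If a lower rescue dose was intended, delete *same*, state the dose on its own, and restate the maximum to fit. At 0.01 mg/kg, a cap taking effect at 100 kg like the study-drug caps would be 0.01 × 100 = 1 mg.

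The cost is a one-line correction by amendment. The sample size is set by funding (G1) and does not change; nor does the schedule of VAS and vital-sign measurements.
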